9.4.2. Secondary Analyses

Treatment comparison between baricitinib dose regimens (4-mg or 2-mg) and placebo for the change from baseline in SLEDAI-2K score at Week 24, and the change from baseline in patient's global assessment of disease activity at Week 24 will be analyzed using MMRM method with treatment, baseline disease activity (SLEDAI-2K <10 versus SLEDAI-2K \geq 10), baseline anti-dsDNA status (positive; negative), region, visit, and the interaction of treatment-by-visit as fixed factors. An unstructured covariance matrix will be used to model the within-patient variance-covariance errors. Type III sums of squares for the LS means will be used for the statistical comparison; the 95% CI will also be reported. Treatment group comparisons with placebo at Week 24 and other visits will be tested.

Treatment comparison between baricitinib dose regimens (4-mg or 2-mg) and placebo for the proportion of patients achieving a SRI-4 response and for the proportion of patients achieving a reduction of \geq 4 points in SLEDAI-2K score at Week 24 will be analyzed using the logistic regression model with treatment, baseline disease activity (SLEDAI-2K <10 versus SLEDAI-2K \geq 10), baseline anti-dsDNA status (positive; negative), and region in the model. The proportions and 95% CI will be reported. Missing data will be imputed using the NRI method.

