Treatment comparisons of continuous efficacy and health outcome variables will be made using mixed-effects models for repeated measures (MMRM) model with treatment, baseline score, baseline disease activity (SLEDAI-2K <10 versus SLEDAI-2K ≥10), baseline anti-dsDNA status (positive; negative), region, visit, and the interaction of treatment-by-visit as fixed factors. An unstructured covariance matrix will be used to model the within-patient variance-covariance errors. Type III sums of squares for the least squares (LS) means will be used for the statistical comparison; the 95% CI will also be reported. Treatment group comparisons with placebo at Week 24 and other visits will be tested.

Fisher exact test will be used for all adverse events (AEs), baseline, discontinuation, and other categorical safety data. Continuous vital signs and laboratory values will be analyzed by an analysis of covariance (ANCOVA) with treatment and baseline values in the model. Other continuous safety variables will be analyzed by t-tests, unless otherwise stated.

2. Introduction

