8.9.1. Patient's Global Assessment of Disease Activity

The Patient's Global Assessment of Disease Activity is a single-item, patient reported scale developed for the assessment of the patient's overall rating of their disease activity due to SLE. The scale measures disease activity through a 5 point Likert scale ranging from 0 ("No disease activity") to 4 ("Severe disease activity") at its worst over the past 7 days (Felson et al. 1993; van Tuyl and Boers 2012).

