9.2.1. General Considerations for Analyses

In general, continuous data will be summarized in terms of the mean, standard deviation, minimum, maximum, median, and number of observations. Categorical data will be summarized as frequency counts and percentages.

Comparisons between the baricitinib 4-mg or baricitinib 2-mg and placebo groups will be performed for all analyses for the Double-Blinded Treatment Period. No adjustment for multiplicity will be done for these comparisons.

Treatment comparisons of categorical efficacy variables will be made using a logistic regression analysis with treatment, baseline disease activity (SLEDAI-2K < 10 versus SLEDAI-2K ≥ 10), baseline anti-dsDNA status (positive; negative), and region in the model. The proportions and 95% confidence interval (CI) will be reported. Missing data will be imputed using the NRI method.

Treatment comparisons of continuous efficacy and health outcome variables will be made using mixed-effects models for repeated measures (MMRM) model with treatment, baseline score,

baseline disease activity (SLEDAI-2K <10 versus SLEDAI-2K ≥ 10), baseline anti-dsDNA status (positive; negative), region, visit, and the interaction of treatment-by-visit as fixed factors. An unstructured covariance matrix will be used to model the within-patient variance-covariance errors. Type III sums of squares for the least squares (LS) means will be used for the statistical comparison; the 95% CI will also be reported. Treatment group comparisons with placebo at Week 24 and other visits will be tested.

Fisher exact test will be used for all AE, baseline, discontinuation, and other categorical safety data. Continuous vital signs and laboratory values will be analyzed by an analysis of covariance (ANCOVA) with treatment and baseline values in the model. Other continuous safety variables will be analyzed based on t-tests, or as otherwise stated.

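### The MMRM in Section 9.4.2 for the two continuous secondary endpoints omits the baseline score that Section 9.2.1 and the synopsis include, which costs precision and leaves the estimates open to chance baseline imbalance

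*Protocol*

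**What the plan says.** Section 9.2.1 sets the rule for all continuous efficacy and health outcome measures: "mixed-effects models for repeated measures (MMRM) model with treatment, baseline score", followed by the SLEDAI-2K category, anti-dsDNA status, region, visit and treatment-by-visit. The Statistical Analysis part of the synopsis gives the same list: "MMRM) model with treatment, baseline score, baseline disease activity (SLEDAI-2K <10 versus SLEDAI-2K ≥10" and so on. In both places baseline score stands alongside the SLEDAI-2K category, so the category was not meant to replace it.

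Section 9.4.2 then names two endpoints, "the change from baseline in SLEDAI-2K score at Week 24" and "the change from baseline in patient's global assessment of disease activity at Week 24". It writes the model out again in full: "analyzed using MMRM method with treatment, baseline disease activity (SLEDAI-2K <10 versus SLEDAI-2K" ≥10, then anti-dsDNA status, and finally "region, visit, and the interaction of treatment-by-visit as fixed factors". Baseline score is absent. The other terms, the unstructured covariance and the Type III tests match 9.2.1. Section 9.4.2 does not refer back to 9.2.1 and gives no reason for a different model.

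**The concern.** The two sections give different estimates, intervals and p-values for the same two endpoints. Nothing in the protocol says which section prevails. A reader who takes the endpoint-specific section as controlling fits the model without baseline.

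That model is the weaker one. A change score that is not adjusted for its own baseline generally has a larger residual variance. A chance baseline difference between arms also carries into the estimated effect through regression to the mean. Patient's Global Assessment is a separate patient-reported item, scored on "a 5 point Likert scale ranging from 0" to 4 (Section 8.9.1), so the SLEDAI-2K category does not stand in for its baseline. For SLEDAI-2K, inclusion criterion 7 requires a clinical score of at least 4 and sets no upper limit. The <10 / ≥10 split therefore treats 4 and 9 alike, and 10 and any higher score alike.

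The protocol's own practice elsewhere points the same way: vital signs, laboratory values and QIDS-SR16 are analysed by ANCOVA with the baseline value in the model (Sections 9.2.1, 9.5, 9.5.2 and 9.5.3). Under 9.4.2 as written, these safety measures are adjusted for baseline and the continuous secondary efficacy endpoints are not.

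**Working it through.** **The plan's own figure.** Section 9.1 states about 81% power with 100 per arm, 40% versus 60% remission and a two-sided 5% chi-square test.

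z = (√100 × 0.20 − 1.96 × √(2 × 0.5 × 0.5)) / √(0.4 × 0.6 + 0.6 × 0.4) = (2 − 1.386) / 0.693 = 0.886, so power = 81.2%. This reproduces the stated figure. It concerns the binary primary endpoint only; the protocol gives no power, SD or correlation for the continuous secondary endpoints.

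**Inputs.** n = 100 per arm (Section 9.1). *Assumptions, not in the protocol:* correlation ρ between baseline and Week 24 of 0.3 to 0.7; equal variance (set to 1) at the two times; normal scores; complete data at one visit; 10 at the median of baseline SLEDAI-2K; and the SLEDAI-2K category explaining little of Patient's Global Assessment.

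**Residual variance of the change score.**
- Baseline score in the model (9.2.1): 1 − ρ²
- No own baseline (9.4.2, Patient's Global Assessment): 2(1 − ρ)
- Two-level median split only (9.4.2, SLEDAI-2K): (1 − ρ²) + (1 − ρ)²(1 − 2/π), because a median split explains 2/π = 0.64 of a normal baseline

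The ratio for Patient's Global Assessment is 2(1 − ρ)/(1 − ρ²) = 2/(1 + ρ). The median-split ratio at ρ = 0.5 is (0.75 + 0.25 × 0.363)/0.75 = 1.12.

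| ρ | Patient's Global: variance ratio | SE ratio | SLEDAI-2K: variance ratio | SE ratio |
|---|---|---|---|---|
| 0.3 | 1.54 | 1.24 | 1.20 | 1.09 |
| 0.5 | 1.33 | 1.15 | 1.12 | 1.06 |
| 0.6 | 1.25 | 1.12 | 1.09 | 1.04 |
| 0.7 | 1.18 | 1.08 | 1.06 | 1.03 |

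If 10 falls at the 30th or 70th percentile of baseline SLEDAI-2K, the variance ratios for that endpoint are 1.23, 1.14, 1.11 and 1.08.

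**Effect on power.** Take an effect with 80% power under the 9.2.1 model, that is, 1.96 + 0.84 = 2.80 standard errors. Under 9.4.2, power is Φ(2.80/SE ratio − 1.96). For ρ = 0.3, 0.5 and 0.7 this gives 62%, 68% and 73% for Patient's Global Assessment, and 73%, 75% and 78% for SLEDAI-2K.

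**Simulation check.** With 3,000 runs, 100 per arm and ρ = 0.5, the SE of the treatment difference was 0.144 with no baseline, 0.133 with the split only and 0.126 with baseline score.

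**Chance imbalance.** The baseline difference between two arms of 100 has SE √(2/100) = 0.14 SD, so its 95% range is about ±0.28 SD. An imbalance of 0.2 SD shifts an unadjusted difference in change by (1 − ρ) × 0.2, which is 0.14, 0.10 and 0.06 SD at ρ = 0.3, 0.5 and 0.7.

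**Unequal variances.** With SDs s0 at baseline and s1 at Week 24, the excess variance from omitting baseline is (s0² + s1² − 2ρ·s0·s1) − s1²(1 − ρ²) = (s0 − ρ·s1)². This is a square and cannot be negative. It vanishes only when s0 = ρ·s1. For illustration, at s0 = 0.7·s1 the variance ratio with no baseline adjustment is 1.18, 1.05 and 1.02 at ρ = 0.3, 0.5 and 0.6.

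**The case against.** The strongest reply is that this is a drafting slip. Two of the three statements of the model include baseline score, 9.2.1 covers both endpoints, and nothing says 9.4.2 overrides it. The protocol also leaves analysis details to the SAP (Sections 9.2 and 9.7.1), which was not available here and may settle the model. That is plausible, but the protocol itself states the model twice and differently, so a SAP can agree with only one of the two. A slip is a reason to correct the text.

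Second, the sizes rest on assumptions. The correlation is not in the protocol, equal variances are doubtful for SLEDAI-2K because entry truncates the baseline, nothing places 10 at the median, and a normal approximation is rough for a 0 to 4 item. Any correlation between the SLEDAI-2K category and Patient's Global Assessment would also recover something. This stands: the figures are illustrative, and the loss could be small, particularly for SLEDAI-2K. The direction is not in doubt, because the excess variance is a square.

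Third, the consequence is limited. Randomisation keeps the unadjusted estimate unbiased on average, so the imbalance problem is conditional on the imbalance that occurs. Stratifying by SLEDAI-2K category limits it for that endpoint. The sample size rests on the binary primary endpoint alone. All of this stands, and it keeps the point to the secondary endpoints.

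**Conclusion.** The concern holds. The protocol contradicts itself on the model for two named secondary endpoints, and the version in 9.4.2 is the less precise one. With ρ between 0.3 and 0.7 and equal variances, following 9.4.2 enlarges the standard error by 8% to 24% for Patient's Global Assessment. For SLEDAI-2K the increase is about 3% to 9%, because the retained category recovers part of the adjustment. Both ranges shrink if the baseline SD is below the Week 24 SD. The contradiction is certain from the text; the sizes depend on values the protocol does not give. Each result is read at two-sided 0.05 with no multiplicity adjustment (Sections 9.2 and 9.2.5), which is a further reason not to leave the model open. The point should be corrected but does not threaten the trial's main conclusion.

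**What to change.** In Section 9.4.2, add baseline score after treatment in the MMRM term list, defined as the continuous baseline value of the endpoint being analysed, and keep the SLEDAI-2K category. Alternatively, replace the list with a reference to the model in 9.2.1, so that it is stated once. Check that the SAP carries the same model.

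The cost is one phrase. Both measures are already scheduled at Visit 2 (Appendix 2), and neither the sample size nor the primary analysis changes. The correction should be made before unblinding, so that the model is not chosen with the results in view.

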5.1.2. Enrollment Criteria

Entered patients are eligible for enrollment into the study (eligible for randomization) only if they continue to meet all of the entry criteria above, and meet all of the following enrollment criteria at the time of randomization (Visit 2):

Type of Patient and Disease Characteristics

- [6] Have a positive ANA (HEp-2 ANA titer $\geq 1:80$) and/or a positive anti-dsDNA (≥ 30 IU) as assessed by a central laboratory at screening.

Note: The ANA and/or anti-dsDNA measurement may be repeated once within approximately 2 weeks of the initial value, and the value resulting from repeat testing may be accepted for enrollment eligibility if it meets the eligibility criterion.

- [7] Have a SLEDAI-2K score ≥ 4 based on clinical symptoms (not including lab values) at randomization.
- [8] Have active arthritis and/or active rash as defined by the SLEDAI-2K at randomization.

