6.2. Method of Treatment Assignment

Patients who meet all criteria for enrollment will be randomized in a 1:1:1 ratio (baricitinib 4-mg; baricitinib 2-mg; placebo) to double-blind treatment at Visit 2 (Week 0). Randomization will be stratified by disease activity (SLEDAI-2K <10; SLEDAI-2K ≥10), anti-dsDNA status (positive; negative), and region (defined in the SAP). Assignment to treatment groups will be determined by a computer-generated random sequence using an interactive web-response system (IWRS). The IWRS will be used to assign 2 bottles (Bottle A and Bottle B), each containing 36 double-blind investigational product tablets to each patient, starting at Visit 2 (Week 0), and at each visit through Visit 8 (Week 20). Site personnel will confirm that they have located the correct bottles by entering a confirmation number found on the bottles into the IWRS. Patients will be instructed to take 1 tablet from Bottle A and 1 tablet from Bottle B each day.

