9.1. Determination of Sample Size

Approximately 300 patients will be randomized in a 1:1:1 ratio to the baricitinib 4-mg, 2-mg, and placebo treatment groups. With 100 patients per treatment group, this study will have approximately 81% power to detect a difference between baricitinib 4-mg or 2-mg and placebo of $\geq 20\%$ in remission rates of rash and/or arthritis at Week 24. The sample size was determined based on the chi-square test with 2-sided type I error of 5% and 40% remission rate of rash and/or arthritis in placebo treatment group. The sample size calculation was performed using nQuery® Advisor 7.0 software.

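### The logistic models for SRI-4 and the 4-point SLEDAI-2K reduction use baseline SLEDAI-2K only as a two-level factor: valid, but a small gain from adding the score is left unused

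*Protocol*

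**What the plan says.** Protocol Section 9.4.2 names the covariates of the logistic model for SRI-4 and for the proportion with a fall of at least 4 "points in SLEDAI-2K score at Week 24 will be analyzed using the logistic regression model with treatment, baseline disease activity (SLEDAI-2K <10 versus SLEDAI-2K" 10 or more), followed by anti-dsDNA status and region. Section 9.2.1 sets the same pattern for every binary efficacy outcome: "Treatment comparisons of categorical efficacy variables will be made using a logistic regression analysis with treatment, baseline disease activity", again as the two-level split. The synopsis repeats it. No section puts the baseline score itself into a logistic model.

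The two-level term is the randomisation factor of Section 6.2: "Randomization will be stratified by disease activity (SLEDAI-2K <10; SLEDAI-2K ≥10), anti-dsDNA status (positive; negative), and region (defined in the SAP").

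For continuous outcomes, Section 9.2.1 specifies "mixed-effects models for repeated measures (MMRM) model with treatment, baseline score" and the two-level category side by side.

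Criterion [7] in Section 5.1.2 requires a SLEDAI-2K score of at least 4, "based on clinical symptoms (not including lab values) at randomization".

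**The concern.** The reduction endpoint is a fixed 4-point fall, and SRI-4 requires the same fall. Section 4.3 reports that in two earlier Phase 3 lupus trials fewer than 1% of patients met the SLEDAI part of SRI-5 but failed on BILAG or the physician's global. It is therefore reasonable to expect SRI-4 to be driven mainly by its SLEDAI part as well.

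The starting score should bear on how easily 4 points are lost. A patient with a total of 4 responds only by reaching 0, whereas a patient at 9 need only reach 5. The planned model treats the two as alike, and the randomisation balances the score only across the cut at 10. What is at stake is some power in two of the four secondary efficacy endpoints, from a measurement already taken at baseline.

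**Working it through.** **Inputs from the protocol (Section 9.1).** 100 patients per arm; "chi-square test with 2-sided type I error of 5% and 40% remission rate of rash and/or arthritis in placebo treatment group"; a 20-point difference, hence 60% on active; stated power about 81%. These rates are for the primary endpoint. None are given for the two responses here, so 40% versus 60% is borrowed.

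**Assumed, because the protocol gives no figure.** Baseline score distribution, strength of its association with response, and the share of patients counted as nonresponders by imputation.

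**1. The plan's own figure.** Power = Φ{[0.20·√100 − 1.96·√(2·0.5·0.5)] / √(0.4·0.6 + 0.6·0.4)} = Φ{(2 − 1.386)/0.693} = Φ(0.886) = 81.2%. The stated 81% is reproduced.

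**2. What the split leaves unused.** In a simulated distribution with mean 9.3, SD 3.56 and 61% below 10, the split retains 62.5% of the score variance, so 37.5% lies within strata. The SD of the between-arm difference in mean baseline score is √(2/100 × 0.375) = 0.087 score SDs (0.086 simulated), and 0.086 × 3.56 ≈ 0.3 points. If the odds ratio per SD is 2, this moves the risk difference by about 0.086 × ln 2 × 0.24 = 0.014 (1.4 percentage points, as an SD). The standard error of the risk difference is √(0.24/100 + 0.24/100) = 0.069, or 6.9 points.

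**3. Latent-change model, no nonresponder imputation.** Week 24 change = arm intercept − slope × (baseline − mean) + normal error with SD 3; response if the change is −4 or lower; 3000 trials per row. Sample-size equivalent = squared ratio of mean z.

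| Slope | Placebo response at baseline 4 / 9 | Power, split only | Power, split + score | Squared z ratio |
|---|---|---|---|---|
| 0 | score has no effect | 81.1% | 80.8% | 1.00 |
| 0.25 | 24% / 39% | 81.4% | 81.9% | 1.02 |
| 0.5 | 13% / 38% | 84.5% | 86.6% | 1.05 |
| 0.75 | 6% / 37% | 88.3% | 90.6% | 1.08 |

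A repeat of this model gave about 1%, 5% and 8% for the three non-zero slopes.

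**4. Same model with nonresponder imputation.** Section 9.2.4 counts treatment discontinuers and patients who escalate background therapy as nonresponders. With 20% such patients in each arm, unrelated to baseline, and overall rates kept at 40% and 60%, the equivalents fall to about 1%, 2% and 2 to 3%. Power changes by −0.3, +0.7 and +1.5 points.

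**5. Logistic model, odds ratio per SD assumed, 4000 trials each.** The variance ratio is that of the standardised risk difference, with the score over split only.

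| OR per SD | Variance ratio | Power, split → with score |
|---|---|---|
| 1.0 | 1.003 | 83.3% → 82.0% |
| 1.25 | 1.001 | 84.1% → 83.3% |
| 1.5 | 0.995 | 82.8% → 82.3% |
| 2.0 | 0.979 | 83.0% → 84.7% |
| 3.0 | 0.947 | 86.4% → 88.2% |

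Under no treatment effect the planned model rejects in 4.8% (OR 1.5) and 4.4% (OR 3.0) of trials.

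**6. Item-based model, anti-dsDNA also adjusted, 3000 trials each.** Scores are built from SLEDAI items, with arthritis, rash, alopecia and ulcer prevalences near those in Section 4.3 and the rest assumed. Placebo response rises from 0.20–0.25 at score 4 to 0.56–0.68 at score 16. Under three levels of between-patient heterogeneity the variance ratios are 0.987, 0.988 and 0.994. Power goes from 82.6% to 83.1%, 82.3% to 82.3%, and 82.6% to 82.1%.

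Monte Carlo error on each power is about 0.6 to 0.7 points. Region was not simulated.

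**The case against.** The covariates are exactly the randomisation factors and are the same for every binary endpoint, so the logistic text contains no error or contradiction. That stands.

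The contrast with the MMRM is weaker than it looks. Section 9.2.1 includes the baseline score, but the MMRM sentence in Section 9.4.2, for change in SLEDAI-2K itself, omits it. Within 9.4.2 the two model types are treated alike. That mismatch between 9.2.1 and 9.4.2 is a separate matter.

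SLEDAI-2K is a weighted presence/absence index, so 4 points are lost by whole items resolving, not by travelling a continuous distance. Criterion [7] also concerns the clinical score only, while the total that defines response includes laboratory items. Both are fair, and the item-based model, which reflects them, gives a variance gain of only about 1%.

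Adding the score might also cost power if it is not prognostic. One paired comparison at slope 0 showed a loss of about 1 point, and the logistic model shows a similar drop at OR 1.0. The squared mean-z ratio there is 0.999, and rejection under no treatment effect is 5.2% for the planned model against 5.0% with the score. The drop therefore looks like discreteness of the test rather than lost information.

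A reader might infer that chance imbalance inside the under-10 stratum biases the estimate. It does not: it is random variation of about 1.4 points beside a standard error of 6.9, already covered by the confidence interval. A reader might also infer a general defect in all responder analyses based on change in a score. No calculation here supports that for CLASI or joint counts.

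**Conclusion.** The point holds as a small efficiency gain in two secondary endpoints. The planned analysis is valid. Adding the baseline score is worth about 0 to 8% in sample size without nonresponder imputation and about 0 to 3% with 20% imputed, which is at most about 2 power points. A weakly prognostic score (odds ratio per SD of 1.5 or less) gives no visible gain. These figures depend on an assumed score distribution, assumed prognostic strength and response rates borrowed from the primary endpoint. The protocol supplies none of the three for these responses.

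Precision is the literal word only for the standardised risk difference. On the log-odds scale the benefit appears as power, not as a smaller standard error.

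**What to change.** In Section 9.4.2, add the baseline SLEDAI-2K score as a continuous covariate to the logistic models for SRI-4 and for the reduction of at least 4 points, and keep the three stratification factors. Specify it before unblinding, since adding a covariate afterwards would be open to challenge. The cost is one sentence and one model degree of freedom. No new data are needed, because the Schedule of Activities already records SLEDAI-2K at Visit 2. Extending the rule in Section 9.2.1 to other responses defined by change in a score is optional. Priority is low.
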